(Round 2) Pre-Analysis Plan

COVID-19 Health Messaging to Underserved Communities

This Draft: September 4, 2020

1. Introduction

The aim of this study is to build on results from our first experiment and test how acknowledging institutional racial injustice affects informational messaging. In particular, we will investigate how well study participants retain knowledge and update beliefs and behavior with respect to COVID-19. We will also test the effect of race concordance of providers with recipients, and whether highlighting the unequal burden of the disease has additional effects on knowledge, beliefs and behavior regarding COVID-19.

Compared to the first study, there are four additional changes to the experimental design of note: 1) the sample will include white respondents in addition to African American respondents;¹ 2) the group that does not view videos about COVID-19 will watch a set of placebo videos about non-COVID health topics; 3) we are collecting follow-up behavioral data from a subset of participants;² 4) this study does not include a few of the treatment variants from the first – specifically, there is no acknowledgment by doctors in the videos discussing health behaviors, and there is no treatment arm to alter perceptions of whether mask-wearing is socially-acceptable.

2. Treatments, and Experimental Protocols

2.1 Treatments

Each subject receives one AMA statement and then watches three videos pertaining to health. The AMA statement either addresses racial injustice (treatment [RI]) or drug pricing (placebo [DP]). The videos pertaining to health behavior either discuss COVID-19 and prevention (treatment) or other non-COVID-19 related issues (control).

- AMA Statement:

RI: Racial Injustice

DP: Drug Pricing

- Treatment Videos

¹We continue to focus our sample on individuals with less than college education.

²We are also collecting baseline measures of these behaviors.

1. Video T1:
 - Introduction
 - Discussion of symptoms
 2. Video T2:
 - Information about social distancing and hygiene
 - Sub-treatment T2A:
 - * Acknowledgment of racial disparities in contagion and mortality.
 3. Video T3:
 - Information about masks
- Placebo Videos
 1. Video C1:
 - Information about fitness routines
 2. Video C2:
 - Information about sleep hygiene
 3. Video C3:
 - Information about sugar intake

We are varying five aspects of the videos across treatments:

[figure not shown]
1. AMA statement regarding racial injustice or transparency in drug pricing.
2. Racial concordance with AMA spokespeople in the videos.
3. Racial concordance with partner doctors in the videos.
4. Informative videos about COVID-19 or non-COVID-19 issues.
5. Video T2 content:
 - Standard message about hygiene and social distancing
 - Previous message, plus acknowledgment of racial disparities in contagion and mortality.

All of the video scripts can be found in Appendix Section A. Figure 1 shows how these different treatments are incorporated in the randomization design.

2.2 Recruitment and Sampling

We are using Lucid to recruit a sample and to compensate subjects for their participation. Our total target sample size is 20,000 subjects, 10,000 African American respondents, and 10,000 White American respondents. We require all participants to be age 18 or older, and we are targeting individuals who have *not* completed a college degree.

Figure 1: Treatment Design

Note: There are 5 randomization instances summarized in this diagram. For the fully extended tree with all 24 final individual cells, see Figure 2.

2.3 Experimental Protocols and Treatments

Our experiment has the following structure:

1. Recruitment and Baseline survey
 - (a) Recruit target sample via Lucid
 - (b) Collect demographic information, political views, and mask ownership. Several demographics variables are being collected directly by Lucid.
2. Randomize subjects to treatment
 - Treatment scripts are tailored to each racial group
 - Within racial group, treatment is stratified on age, gender and geographic region.
 - Randomization is at the individual level according to Figure 1.
 - There will also be a control group who will not receive COVID-19 videos, but will receive information at the very end of the survey.
3. Video delivery for all individuals.
 - (a) After each of the three videos, respondents evaluate the video's usefulness, and trustworthiness, along with the respondents intention to follow the advice in the video and share information from the video.
4. Endline survey
5. Debrief script

6. Follow-up survey

- (a) We will follow up with participants three days post-treatment.
- (b) The chief purpose would be to measure health-seeking and health-preserving behaviors.

3. General Hypotheses to be Tested

This section lists the general hypotheses we want to test. For those, we are planning to run broadly pooled treatments (and specific interactions specified below). Main hypotheses:

1. Baseline treatment effect: Does any COVID-19 message affect knowledge/intended behavior/priorities in donations/actual behavior?
 - (a) Compare the effectiveness of any doctor treatment video vs. any doctor placebo video.
 - We will test this in the full sample and in the white and African American samples, separately.
2. Concordance effect: Does the concordance of the doctor in the COVID-19 video affect the impacts of the message?
 - (a) Within the treatment group receiving a COVID-19 doctor video, compare the effectiveness of the video if the respondent is randomized to a doctor of concordant vs. discordant race.
 - We will test this hypothesis separately in the white and African American samples. If the effects go in the same direction for both populations, we will also test this hypothesis in the full sample.
 - An alternate way to define concordance is whether the subject views a racially concordant messenger both (or either) in the COVID-19 doctor video and in an AMA statement of any kind. We will also test the effectiveness of the messaging under this alternate measure.
3. AMA acknowledgement: Does the AMA message mediate the impacts of the COVID-19 messaging or of the racial concordance of the messenger?
 - (a) Compare baseline treatment effect [1] for AMA acknowledgement vs AMA placebo.
 - (b) Compare concordance effect [2] for AMA acknowledgment vs AMA placebo. Is the concordance of the doctor in the COVID-19 video more or less important when there is an AMA message vs. the AMA placebo?
 - We will test these hypotheses separately for white and African American respondents.
4. Does the racial concordance of the AMA messenger matter?
 - (a) Compare whether AMA acknowledgement [3a] is more effective if the AMA messenger is racially concordant.

- (b) Compare AMA acknowledgement effect [3b] by racial concordance of AMA messenger. Is the concordance of the doctor in the COVID-19 video more or less important when there is a racially concordant AMA message vs. a non-racially concordant AMA message?
 - We will test these hypotheses separately for white and African American respondents.
5. Content of message: does the mention of the racial disparities (video 2RD) in disease burden affect knowledge/intended behavior/ priorities in donation/actual behavior?
- (a) Within the COVID video treatment group, compare videos with RD information vs. no RD information.
 - (b) Within the COVID video treatment group, how does information about RD interact with the racial concordance of the doctor messenger? Does information about RD make racial concordance more important, especially among African American respondents?
 - (c) Within the COVID video treatment group, how does information about RD interact with the AMA racial injustice message? Does information about RD make the AMA acknowledgement more effective, especially among African American respondents?
 - (d) We are also interested in how information about RD mediates Hypotheses 3b, 4a, 4b, and 4c.
 - In addition to the standard outcomes, we are also particularly interested in impacts on donations to a COVID fund that is specifically for African Americans vs. a general COVID fund. We also are interested in how this information changes perceptions of the policy responses of state and federal governments.
 - For 5a, we are interested in the white and African American groups, separately, and also the full, pooled sample. For 5b and 5c, we are mainly interested in the effects separately for white and African American respondents.
 - RD should have the largest impacts for individuals who have incorrect beliefs. Moreover, the impacts of the information should be different for individuals with priors about relative impacts on African Americans that are too low versus too high. (See Section 5.4, below).

4. Data Collection and Outcomes

We will run our experiment beginning on August 7, 2020. We are recruiting individuals that fit our screening criteria from an online survey firm. The data will be collected from respondent surveys. There is a short baseline module before individuals are exposed to the videos. Following the final video, there is an endline outcome module that all participants complete. Respondents also evaluate each video immediately after watching it. We also plan to follow up with individuals a few days after the treatment delivery for an additional survey to measure whether the videos changed behaviors. Prior to treatment, we ask all participants whether they would be willing to answer the follow-up survey. We allow individuals to enroll in the study, independent of their follow-up availability. We plan to control for willingness to answer a follow-up in all regressions. All of the survey responses will be downloaded in a .csv file for cleaning and analysis in R.

4.1 Baseline Survey Variables

The baseline information for all respondents includes the following demographic characteristics:

- Education
- Age
- Location
- Sex
- Political Views

We elicit additional health information at baseline, but participants may choose not to answer these questions:

- Mask Ownership
- Public Excursions
- Health Behavior

See Section 5, below for a summary of our key endline survey variables.

4.2 Data quality checks

We have several questions in the survey that capture respondent attention. We use some of these questions to screen out low-attention survey takers before assigning treatment. We further plan to exclude those that take very little time on the survey overall and/or on the videos.

5. Empirical Analysis

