5.1 Balance Checks

We will conduct a series of balance tests across treatment arms to ensure that there are no chance differences between subjects in the various arms. We will regress characteristics measured pre-treatment on indicators for the arms and test their individual and joint significance. Balance tests will be conducted using all of the variables measured in the baseline survey.

We will also test for balance in attrition rates (see Section 6.2, below).

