6.2 Attrition

We have two separate endline surveys. The first will take place immediately after treatment delivery. The type of attrition that might arise here is through dropping out of the online session before completing all of the survey questions. To try to limit differential attrition, we are showing placebo videos to the control group to fill approximately the same amount of time.

Our second set of endline outcomes will take place a few days after the main survey. Lucid, the survey firm, will try to recontact a specified list of initial participants. We are only expecting modest recontact rates, and therefore high levels of attrition. Importantly, to try to limit differential attrition, all individuals will be recontacted with the exact same message, and it will not be made salient that the survey is a direct follow-up to the previous study.

We plan to test for differential attrition at both endlines across our key comparison groups.

7. Funding and Human Subjects Review

Funding is provided by the National Science Foundation RAPID-2029880 for Covid-19 research, and RAI Italian Broadcasting corporation (via an unrestricted gift to J-PAL that we attributed to this project). The IRB at MIT is serving as the primary institution of record and has entered into a reliance agreement with Harvard, Massachusetts General Hospital, and Yale. We have also received IRB approval from Stanford.

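### Respondents are dropped for speed measured wholly or largely after randomisation, and no analysis without that exclusion is planned, so randomisation no longer guarantees comparable analysed arms

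*Combined protocol and SAP*

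**What the plan says.** Section 4.2 describes two separate steps. The first is an attention screen: "We use some of these questions to screen out low-attention survey takers before assigning treatment". That step comes before assignment and is not in question. The second is the speed rule: "We further plan to exclude those that take very little time on the survey overall and/or on the videos". It gives no threshold, and its wording leaves open whether total time, video time or both will be used.

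Section 2.3 gives the order: baseline survey, randomisation, videos with an evaluation after each, then endline. On assignment it says "Randomization is at the individual level according to Figure 1". Section 4 adds "There is a short baseline module before individuals are exposed to the videos".

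Three other provisions bear on the point:

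- Section 5.1: "We will regress characteristics measured pre-treatment on indicators for the arms and test their individual and joint significance". It does not say whether this is done before or after the speed exclusion.
- Section 5.3: double-lasso selection of controls.
- Section 6.2: tests of differential attrition at both endlines. For the first endline, attrition is described thus: "The type of attrition that might arise here is through dropping out of the online session before completing all of the survey questions". For the follow-up it is failure to recontact. On the placebo, the section says "we are showing placebo videos to the control group to fill approximately the same amount of time".

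No section plans an estimate that keeps the fast respondents.

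**The concern.** Randomisation makes the arms comparable as assigned. A filter applied afterwards preserves that only if it acts alike in every arm. Here the filter is time spent on the assigned videos, and on a survey that consists mostly of those videos and the questions after them. Assignment can therefore affect who is kept, either through the share excluded or through the type of person excluded.

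If exclusion is unrelated to arm, the comparison stays unbiased. If it is related, the estimate carries a bias that a larger sample does not shrink, while the standard error at 20,000 respondents is small. The plan as written would show this only in part, through balance on measured traits.

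**Working it through.** The plan states no exclusion rate, cut-off or type I error to reproduce. The check has three parts.

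**1. Timing.** From Sections 2.3 and 4, only the short baseline module precedes assignment. The videos, the three evaluations and the endline module all follow it.

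**2. Could the arms differ in time?** Words in the Appendix A scripts, each bracketed placeholder counted as one word:

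- COVID: T1 176 + T2 220 + T3 118 = 514; with the 30-word T2A segment, 544.
- Placebo: C1 127 + C2 144 + C3 133 = 404.
- Ratios: 514/404 = 1.27 and 544/404 = 1.35.

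Words are only a proxy, because running times are not given.

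**3. Size, under a true null.** From the documents: 10,000 respondents per race (Section 2.2) and 24 cells (note to Figure 1). Those cells factor as 2 AMA statements × 2 AMA messengers × 2 doctors × 3 video sets, so 16 of the 24 are COVID cells. Assumed: either two-thirds on COVID videos (equal cells) or half (a 1:1 split), a two-sided 5% test, the exclusion rates, and the outcome gaps.

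Let e be the share excluded and g the retained mean minus the excluded mean, in SD. The retained mean exceeds the full-arm mean by e·g, so:

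- bias (COVID minus placebo) = e₁g₁ − e₀g₀
- SE = √[1/(n₁(1−e₁)) + 1/(n₀(1−e₀))]
- type I error = P(|N(bias/SE, 1)| > 1.96)

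Sizes are 6,667 vs 3,333 (one race) and 13,333 vs 6,667 (pooled), or 5,000 vs 5,000 and 10,000 vs 10,000 with half on COVID. The higher exclusion rate is put in placebo, where the scripts are shorter. Bias is shown as an absolute value.

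| Excluded, placebo vs COVID | Gap (SD) | Bias (SD) | Two-thirds: one race / pooled | Half: one race / pooled |
|---|---|---|---|---|
| 3% vs 2% | 0.3 | 0.003 | 5.2% / 5.4% | 5.3% / 5.5% |
| 3% vs 2% | 0.5 | 0.005 | 5.6% / 6.2% | 5.7% / 6.4% |
| 10% vs 8% | 0.3 | 0.006 | 5.8% / 6.7% | 5.9% / 6.9% |
| 12% vs 8% | 0.5 | 0.020 | 14.5% / 24.3% | 15.8% / 26.9% |
| 8% vs 8% | 0.5 vs 0.25 | 0.020 | about 15% / 25% | about 16% / 27% |

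For the 12% vs 8% row: bias = 0.12×0.5 − 0.08×0.5 = 0.020. With two-thirds on COVID, SE = 0.0224 (one race) and 0.0159 (pooled). On an indicator with 50% prevalence (SD 0.5), 0.020 SD is 1 percentage point. The last row has equal exclusion rates, so a test of rates would not reveal it.

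Three things reduce these figures:

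- **Controls.** If they absorb half the 0.5 SD gap, the 12% vs 8% row falls to 7.3% / 9.7% (two-thirds) or 7.6% / 10.3% (half).
- **Follow-up outcomes.** Section 6.2 says "We are only expecting modest recontact rates, and therefore high levels of attrition". At an assumed 20% to 50% recontact, equal across arms, the same row with two-thirds on COVID gives 6.8% to 9.7% (one race) and 8.7% to 14.5% (pooled).
- **The safety index.** Section 5.2 defines it as a within-person change, so stable level differences largely cancel and the figures are an upper guide.

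**The case against.** The strongest reply is that bias is possible but not shown. No exclusion rate or outcome gap is documented, and the three milder cases are close to nominal. The figures near 25% need a 4-point difference in exclusion with a 0.5 SD gap, or a twofold difference in gap at equal rates, together with pooled races, first-endline outcomes and no help from controls. All of this stands. The table is an illustration and bounds nothing in either direction.

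The word counts are also weak evidence. Section 6.2 says the placebo runs for roughly the same time, and a cut-off set relative to each video's length would largely close that route. This stands too, but Section 4.2 specifies no such cut-off, and matched duration does not ensure that the same kind of person hurries in each arm. For the concordance, disparity and AMA contrasts, differential exclusion is possible but nothing in the documents points to it.

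The attrition and balance tests might be read as covering exclusions. Section 6.2 describes only drop-out and non-recontact. Balance tests and lasso controls work on measured traits, and the tests help only if run on the analysed sample.

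Finally, removing inattentive respondents is a reasonable data-quality aim, and keeping them dilutes effects. Which estimate should lead can be debated. The case for reporting both, with exclusions by arm, does not depend on that choice.

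**Conclusion.** The concern holds. The plan conditions its analysed sample on a measure that the assigned arm can affect, and it provides no estimate free of that condition. This follows from the plan's own sequence and needs no assumption about respondents.

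The size of any bias is unknown and may be negligible. The span of about 5% to about 27% belongs to the cases chosen and rests on the assumed exclusion rates, gaps and allocation. COVID versus placebo is the most exposed comparison. The point should be fixed because the current plan would show a problem only in part and the repair is cheap.

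**What to change.** Make the primary analysis all randomised respondents who passed the pre-assignment attention screen and have the outcome, in their assigned arm, with no exclusion on time measured after randomisation. State that this set still depends on outcome availability and so must be read beside the attrition tests.

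Report the speed-excluded estimate as a sensitivity analysis, with the criterion and cut-off fixed in advance. For it, give:

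- exclusion counts by arm and a test of exclusion rates by arm;
- baseline characteristics of excluded respondents by arm;
- the Section 5.1 balance tests, run on the analysed sample.

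Alternatively, base any speed screen only on pages completed before randomisation.

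The cost is SAP wording and one table, with no new data. The table would be informative. For 3% vs 2% excluded, z = 0.01/√(0.02×0.98/6,667 + 0.03×0.97/3,333) = 2.93, or about 83% power in one race. Pooled, z = 4.14, or 98.5%. It would miss a difference in type of person at equal rates, hence the baseline comparison. The drawback is modest dilution from keeping inattentive respondents, about 10% if 10% of them have zero effect. The sensitivity analysis would show it.

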5.1 Balance Checks

We will conduct a series of balance tests across treatment arms to ensure that there are no chance differences between subjects in the various arms. We will regress characteristics measured pre-treatment on indicators for the arms and test their individual and joint significance. Balance tests will be conducted using all of the variables measured in the baseline survey.

We will also test for balance in attrition rates (see Section 6.2, below).

5.2 Key Outcomes

We intend to measure the treatment effects on the following set of outcomes:

1. The number of participants with knowledge of COVID related symptoms and transmission as assessed by a questionnaire we've developed specifically relevant to the intervention videos we are using for the project. Specifically, we define the following three outcomes, measured both at first contact and followup:

- Knowledge of COVID symptoms: participants are asked to identify 4 symptoms of COVID from a list of 9. We will define an indicator for whether participants select the 3 most common symptoms (fever, cough, difficulty breathing).
 - Knowledge of COVID prevention: participants are asked to identify 3 COVID prevention behaviors from a list of 7. We will define an indicator for whether participants select the 3 behaviors emphasized in the videos (staying outside and 6ft from others; washing hands when going and coming from home; mask wearing).
 - Knowledge of asymptomatic infection: an indicator for whether participants correctly answer that COVID can spread asymptotically.
2. Behavioral outcome 1: Number of participants who report behavior change related to messages provided in the intervention videos; measured via a specific questionnaire instrument we've developed to correspond to the intervention. Specific behaviors include physical distancing, mask wearing, and hand hygiene. Since we ask about several safety behaviors, we will define a standardized index to combine them into one measure, calculated at both first contact and endline. The key outcome is the within-person change in this safety index from first contact to endline.
 3. Behavioral outcome 2: Revealed preference estimate of willingness to pay for masks. The subjects will trade-off the willingness to get a pair of masks or an amazon gift card when participating in a strategy-proof lottery.
 4. Behavioral outcome 3: Number of links people click on for additional information on the COVID-19 behaviors. Links will include testing locations, state public health hotline, and symptom tracker.
 5. Behavioral outcome 4: Donations to a COVID-related charity. After providing information on the number of weekly COVID cases, we are measuring the willingness to donate to a COVID-related charity vs. a generic health-related charity.
 6. Behavioral outcome 5: Donations to African-American COVID-19 fund. After providing information on the disproportionate burden on African-American communities, we are measuring the willingness to donate to a COVID relief fund that focuses on African-American communities vs. one that generically provides relief to disadvantaged individuals.
 7. Evaluation of state and local COVID policy. We are measuring how well participants think their federal and state governments managed to balance opening the economy and limiting the health impacts of Covid-19. We believe that information about racial disparities, in particular, may change these perceptions, especially for people who believed that racial disparities did not exist or were less severe at baseline.

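### The key behaviour outcome is a change score, so recontacted respondents with no usable baseline index drop out of it, at a cost in precision and coverage but not in comparability of the arms

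*Combined protocol and SAP*

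**What the plan says.** Section 5.2 item 2 combines distancing, mask wearing and hand hygiene: "we will define a standardized index to combine them into one measure, calculated at both first contact and endline". It then fixes the estimand: "The key outcome is the within-person change in this safety index from first contact to endline". Section 5.3 carries changes in reported behaviour into the regressions, with controls chosen by double lasso.

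Section 4.1 lists mask ownership, public excursions and health behaviour under this condition: "We elicit additional health information at baseline, but participants may choose not to answer these questions". Footnote 2 says that baseline measures of the follow-up behaviours are collected, and Section 4.1 lists no other baseline behaviour items.

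The later measurement covers only part of the sample. Section 1 says "we are collecting follow-up behavioral data from a subset of participants". Section 2.3 item 6 puts the follow-up three days after treatment and says of it: "The chief purpose would be to measure health-seeking and health-preserving behaviors". Section 6.2 adds: "We are only expecting modest recontact rates, and therefore high levels of attrition".

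Sections 5.1 and 6.2 plan tests of differential attrition. The plan gives no minimum number of items for the index, no imputation and no rule for a respondent whose baseline index is missing.

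**The concern.** A change score needs both values. Someone who declined the baseline behaviour items but answered the whole follow-up contributes nothing to the outcome as defined. A randomised comparison does not need a baseline value: the arms can be compared on the follow-up index, with baseline used only to reduce noise.

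This is the only outcome in Section 5.2 built from self-reported behaviour, and the follow-up answers it uses are the scarcest data in the study. Losing some of them lowers precision, in an analysis that is mostly run separately by race. It also narrows the result to people willing to report their health behaviour at baseline. This loss comes on top of non-response at follow-up, because these people did respond. A raw change score also carries the noise of both measurements, which is inefficient unless the two are highly correlated.

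**Working it through.** **Inputs.** The documents give a target of 20,000 (10,000 per racial group). They give no skip rate, recontact rate, baseline to follow-up correlation or power calculation for this outcome, so there is no figure of the plan's own to reproduce. Everything below is assumed: skip rate s (share of recontacted respondents with no baseline index) 10% to 30%, with 1% to 3% as a low case; correlation r 0.5 to 0.9; unit variance at each wave; skipping unrelated to the index.

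**Who is lost.** For someone who answers none of the baseline index items, the loss follows from the definition. For a partial skipper it depends on the missing index rule. If one blank voids the index, independent 5% skipping per item loses 1 − 0.95³ = 14% over 3 items and 1 − 0.95⁶ = 26% over 6.

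**Headcount.** With an assumed 20% recontact, 20,000 × 0.20 = 4,000, of whom 400 (s = 10%) to 1,200 (s = 30%) have follow-up answers that go unused.

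**Precision.** Variance of the treatment effect, up to a common factor that cancels in the ratios:

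- A, raw change score, complete cases: 2(1 − r)/(1 − s)
- B, follow-up adjusted for baseline, complete cases: (1 − r²)/(1 − s)
- C, follow-up adjusted for baseline, everyone kept with a missing-baseline indicator, one pooled regression: (1 − s)(1 − r²) + s

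| r | s | A | B | C | SE ratio C to A, √(C/A) | SE ratio C to B, √(C/B) |
|---|---|---|---|---|---|---|
| 0.5 | 10% | 1.111 | 0.833 | 0.775 | 0.835 | 0.964 |
| 0.5 | 30% | 1.429 | 1.071 | 0.825 | 0.760 | 0.877 |
| 0.7 | 10% | 0.667 | 0.567 | 0.559 | 0.916 | 0.993 |
| 0.7 | 30% | 0.857 | 0.729 | 0.657 | 0.875 | 0.950 |
| 0.8 | 10% | 0.444 | 0.400 | 0.424 | 0.977 | 1.030 |
| 0.8 | 30% | 0.571 | 0.514 | 0.552 | 0.983 | 1.036 |
| 0.9 | 10% | 0.222 | 0.211 | 0.271 | 1.104 | 1.133 |
| 0.9 | 30% | 0.286 | 0.271 | 0.433 | 1.231 | 1.263 |

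C to A is the whole effect of the change; C to B isolates keeping the skippers. Baseline adjustment alone (B to A) gives √((1 + r)/2): 0.866 at r = 0.5 and 0.922 at r = 0.7. At 10% skipping it therefore supplies most of the gain.

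**Low skip rates.** At r = 0.5, √(C/B) is √(0.7525/0.7576) = 0.997 for s = 1% and √(0.7575/0.7732) = 0.990 for s = 3%. At r = 0.7 and s = 3% it is √(0.5247/0.5258) = 0.999. The gain from keeping skippers is then 1% or less.

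**High correlation.** Skippers enter without baseline adjustment and raise the pooled residual variance. At r = 0.8 keeping them raises the standard error by 3% to 4% against B, though C is still slightly better than A. At r = 0.9, C is worse than A by 10% to 23%.

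**The case against.** The strongest reply is that the loss is inferred. The plan does not say that skippers are dropped, and it does not list the index items. Mask ownership is not mask wearing, and the optional health-behaviour item is undefined. Footnote 2 and the absence of other baseline behaviour items make the link likely, not certain. This stands, and it rules out saying that every skipper is lost: that is certain only for someone with no usable baseline index.

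A reader might also infer bias between the arms. The documents do not support that. Section 2.3 places the baseline survey before randomisation, and Section 4 places it before the videos, so skipping cannot depend on the assigned arm. Differential non-response at follow-up is a separate matter.

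A reader might further infer that the change is measured minutes after the videos, because Section 6.2 says: "We have two separate endline surveys. The first will take place immediately after treatment delivery". Sections 1, 2.3 and 4 largely settle this by assigning behaviour measurement to the later survey. What remains is loose use of the word endline, which naming the survey corrects.

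If the lasso selects the baseline index, regressing the change on treatment and baseline gives the same treatment coefficient as regressing the follow-up on both. The adjustment gain might then already be available. But selection is not guaranteed, and it would not bring the skippers back.

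Finally, a smaller repair exists: state a missing-item rule. That would rescue partial skippers, but not those with no baseline answers unless it imputed them.

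**Conclusion.** The concern holds in a limited form. As defined, the outcome excludes recontacted respondents who have no usable baseline index; how many partial skippers go with them depends on a rule that the plan does not state. The cost is precision and coverage.

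Against the raw complete-case change score, the alternative lowers the standard error by about 16% to 24% at correlation 0.5 and 8% to 13% at 0.7, for assumed skip rates of 10% to 30%. The part due to keeping skippers is about 4% to 12% and 1% to 5%, and negligible at 1% to 3% skipping. At correlation 0.8 that part reverses, and at 0.9 the whole alternative is less precise than the change score. With a gap of about three days, a high correlation is possible. The coverage argument does not depend on the correlation, but the documents do not show that skippers would respond differently. The change should be made, but the plan is not invalid without it.

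**What to change.** In Section 5.2 item 2:

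- Make the outcome the safety index at the three-day follow-up, naming that survey in place of endline.
- Analyse everyone with a follow-up index, and state how many items an index needs.
- Always include the baseline index as a regressor, outside the lasso selection. Where it is missing, set it to a constant and add a missing-baseline indicator.
- Use robust standard errors.
- Keep the complete-case change score as a sensitivity analysis.

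This needs plan wording and one indicator variable, with no new data. The effect becomes a baseline-adjusted difference at follow-up instead of a raw within-person change. Simple pooling may lose precision if the correlation proves very high, which the sensitivity analysis would help to show. Collection began on August 7, 2020 and this draft is dated September 4, so the change should be dated and made before the behaviour outcome is examined by arm.
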